4 STUDY DESIGN

4.1 Overall Design

This is a study with a 2-part treatment period that will evaluate the potential of tildacerfont to reduce GC burden in adult subjects with classic CAH who have LLD \leq A4 \leq 2.5x ULN and are on supraphysiologic doses of GC therapy (\geq 30 mg/day and \leq 60 mg/day in HCe). The first 24 weeks of the treatment period will be a randomized, double-blind, placebo-controlled study in which subjects are randomized in a 1:1 ratio to receive either placebo or tildacerfont at 200 mg QD. All subjects will receive open-label tildacerfont at 200 mg QD during the remaining 52 weeks of the treatment period. An optional Open-Label Extension Period will provide an open-label treatment with tildacerfont at 200 mg QD for up to 240 weeks.

Refer to the study schematic provided in [Section 1.2](#).

4.1.1 Study Periods

This study will consist of the following periods:

- A \leq 45-day *Screening Period* for confirmation of eligibility
 - Optional A4 Screening Visit.
 - Screening information captured within 45 days of Day 1 in this study (particularly screening information transferred from Spruce Biosciences Study SPR001-203 to this study) will be used to determine eligibility and fulfill screening requirements for this study.

In Germany, screening information from Spruce Biosciences Study SPR001-203 is not permitted to be transferred to determine study eligibility.

A 6- or 12-week *Glucocorticoid Conversion Period* (Week -12 to either Week -6 or Week -2 [\pm 3 days]) for subjects on dexamethasone at the initial Screening Visit who agree to convert to a non-dexamethasone regimen as determined by their physician ([Section 1.3.3](#))

- A 76-week, 2-part *Treatment Period*
 - The 24-week *Placebo-Controlled Treatment Period* (Day 1 to Week 24) will be randomized, double-blind, and placebo-controlled. Subjects will be randomized in a 1:1 ratio to receive either placebo or tildacerfont at 200 mg QD.
 - The 52-week *Open-Label Period* (day after Week 24 to Week 76) will provide subjects who complete the Placebo-Controlled Treatment Period with 52 weeks of open-label treatment with tildacerfont 200 mg QD.
 - Beginning at Week 2 (based on the Day 1 A4 measurement), subjects with an A4 measurement \leq ULN at a study visit will begin to reduce their daily GC dose by increments of no more than 5 mg/day HCe each time, down to a minimum of 15 mg HCe per day. Beginning at Week 6 (based on Week 6 A4 measurement), subjects with an A4 $>$ 1.25x ULN will begin to increase their daily GC dose by increments of no more

than 5 mg/day HCe each time. More details on GC dose adjustments are provided in [Section 4.1.4.3](#).

- Subsequent GC dose adjustments are based on A4 measurements at Weeks 12, 18, 24, 32, 40, 52 and 64.
- For subjects continuing into the optional Open-Label Extension Period
 - The Open-Label Extension Period will provide subjects with up to 240 weeks of treatment with tildacerfont 200 mg QD.
 - Subjects will be eligible to adjust GC dose level at each visit (see [Section 4.1.4.3](#)).
- A 30-day *Follow-up Period at EOT*
 - Subjects who do not continue to the Open-Label Extension Period upon completion of Treatment Period will enter a 30-day Follow-up Period.
 - Upon completion of the Open-Label Extension Period, subjects will enter a 30-day Follow-up Period.
 - At the end of study treatment, subjects will maintain the GC regimen and mineralocorticoid regimen (as applicable) established during the course of the study until the 30-day follow-up visit unless the Investigator determines that the subject's clinical status necessitates a dosing change. After completion of the study, GC therapy will be managed at the discretion of the subject's treating physician.

4.1.2 Study Visits and Telephone Contacts

4.1.2.1 Study Visit Schedule

- During the Screening Period:
 - Optional A4 Screening Visit
 - Screening Visit at ≤45 days before Day 1
- During the Glucocorticoid Conversion Period (for subjects on dexamethasone at Screening): visits at Weeks -12 and -8 (and -2, if applicable); scheduled telephone contacts at Weeks -11 and -6 (and -5, if applicable)
- During the 24-week Placebo-Controlled Treatment Period: visits on Day 1 (baseline) and at Weeks 3, 6, 12, 18, and 24
- During the 52-week Open-Label Period: visits at Weeks 32, 40, 52, 64, and 76; scheduled telephone contacts at Weeks 27 and 46
- During the optional Open-Label Extension Period: Visits every 3 to 6 months at Weeks 88, 100, 124, 148, 172, 196, 220, 244, 268, 292 and 316
- At 30 days after the last dose of study drug for final safety follow-up
- PRN telephone contacts are detailed in [Section 4.1.2.3](#)

4.1.2.2 Mode of Study Visits in the Context of COVID-19 or Other Logistical Challenges

All efforts should be made to conduct visits in the clinic as per the Principal Investigator's clinical judgement or patient's preference. Since the COVID-19 pandemic is expected to continue during the conduct of this trial, study visits can be adapted into a combination of in-

clinic and telemedicine activities, with optional at-home visits, to mitigate the risk of COVID-19 infection associated with study participation and to accommodate local and individual circumstances while maintaining participant access to healthcare resources.

Some of the clinic activities of the Screening Visit may be conducted remotely (at the subject's home) if approved by the site's IRB/EC.

For post-Screening activities, the investigational site will decide how to conduct these activities if alternatives are necessary due to COVID-19 restrictions, taking into consideration subject preference and the relevant local public health guidelines and striving to maintain a consistent mode for each activity throughout the study. The EDC system will capture the mode by which data are collected for each visit/activity.

If home visits are conducted, the qualified medical professionals who will perform the study's home visits are defined as individuals who meet national/local licensing requirements needed to perform the procedures required at the home visits. Their national/local licensure will be verified, and they will complete training on the study protocol and GCP. If the medical professional does not meet the national/local licensing requirements needed to perform the optional home visit activities (physical examination), the Investigator or Investigator-delegated study personnel must complete these activities for each visit.

Refer to [Section 11](#) for more information on study conduct in the context of COVID-19 or other logistical challenges.

4.1.2.3 Telephone Contacts

Sites will make scheduled telephone contacts during the Glucocorticoid Conversion Period at Weeks -11 and -6 (and -5, if applicable) and during the Treatment Period at Weeks 27 and 46 to record any AEs and concomitant medications.

After receiving A4 results from the Day 1 (dose reduction only) and Week 6, 12, 18, 24, 32, 40, 52, and 64 study visits, or during the optional Open-Label Extension Period, sites will make telephone contacts to subjects who are eligible for a GC dose adjustment. Sites will contact these subjects within 2 weeks after each applicable study visit. The site will direct the subject to adjust his/her GC dose at that time if the subject has not experienced any change in clinical status since the previous study visit. If no GC dose adjustment is warranted based on the A4 level, the site does not need to contact the subject. If a subject's GC dose is adjusted, the site will telephone the subject again 7 days after the GC dose adjustment to assess for the occurrence of AEs and the initiation of new concomitant medications.

Subjects should be instructed to telephone sites if they have any concerns about their health.

PRN telephone contacts initiated by sites and telephone contacts initiated by subjects should be captured in the EDC system as "unscheduled" telephone contacts.

4.1.3 Study Diary/Drug Adherence Data Collection

During the Glucocorticoid Conversion and Treatment Periods, subjects will use an electronic study diary to document study drug and background GC adherence. Female subjects will also use the study diary to record menstrual information (including start and stop dates of menses).

4.1.4 Procedures for Glucocorticoids

4.1.4.1 General Procedures for Glucocorticoids

Information to be collected at screening about a subject's current and historical GC therapy during the past year include the type(s) of GC, the regimen(s), reason(s) that the subject is/was on that particular GC regimen, and any GC stress dosing during the past year.

To be eligible to enter this study, subjects must be on a stable dose of GC replacement ≥ 30 mg/day and ≤ 60 mg/day in HCe for ≥ 1 month before screening without any evidence of non-adherence to the GC regimen during this period (stress dosing is allowed). For any subject whose prescribed total daily GC dose varies from day to day but is stable on a weekly basis, an average total daily dose based on the total weekly dose will be calculated to determine eligibility.

Subjects with the salt-wasting form of CAH must also be on a stable dose of mineralocorticoid replacement for ≥ 1 month before screening. A change to a subject's GC regimen during the study could necessitate an adjustment to the subject's mineralocorticoid regimen. The adequacy of a subject's mineralocorticoid dose should be monitored throughout the study and adjusted as needed to adequately maintain standing blood pressure, plasma renin levels, and electrolytes (serum potassium in particular) within acceptable ranges ([Speiser 2018](#)).

Please see instructions for administration of GCs through Week 24 and after Week 24 below.

Administration of GCs through Week 24:

- Participants who enter the study under protocol versions prior to Protocol Version 7.0 will receive Sponsor-supplied GCs
- Participants who enter the study under Protocol Version 7.0 and higher will receive Principal Investigator-prescribed GCs *
- Participants should remain on the same GC (not the same dose) through week 24. If a change is necessary due to drug shortage, etc., switching within the same type of GC (i.e., intermediate – intermediate/prednisone – prednisolone) is allowed. Any such changes should be discussed with the Medical Monitor.

*In countries where prednisolone 1mg is not commercially available, the Sponsor will provide this GC through week 24

Administration of GCs after Week 24:

- Participants who enter the study under any protocol version (1 and higher) will use Principal Investigator-prescribed GCs
- A change in GC type (e.g., prednisone to prednisolone) is acceptable after Week 24 (see note on change between types of GC below)

Subjects should not switch between short-acting and intermediate-acting GCs because it could confound interpretation of morning biomarker levels (e.g., if a subject switches from HC to prednisolone and the morning A4 decreases, it may be difficult to ascertain if the A4 decrease is due to longer GC coverage overnight or study drug effect). Half-lives of intermediate-acting GCs are similar enough that confounding interpretation should not be a concern when switching

from one intermediate-acting GC to another. For example, after Week 24, subjects could switch between prednisone to prednisolone (one intermediate-acting GC for another) but should not switch between short-acting and intermediate-acting GCs unless necessary based on GC availability. Any such cases should be discussed with the Medical Monitor.

Sponsor acknowledges that the protocol uses a 1:4 ratio for HC: prednisone and 1:5 for HC: prednisolone. Transitioning from prednisolone to prednisone will require the closest approximation possible, given the denomination of tablets available. Switching from 1mg prednisolone to 1mg prednisone is the closest approximation possible, and therefore is not a protocol deviation.

On the evenings before scheduled laboratory assessments, subjects should take their evening GC dose before 10 PM. On the mornings of scheduled laboratory assessments, subjects should delay taking any morning dose of GC medication until after the 8 AM (± 1 hour) laboratory assessments have been completed. On all other days during the study, subjects should take their GC medication at the usual times. Mineralocorticoid may be taken at any time of day, but its timing relative to laboratory assessments should be consistent throughout the study.

4.1.4.2 Glucocorticoid Dose Conversion to Hydrocortisone Equivalents

[Table 1](#) defines the potencies of various GCs relative to HC in treating CAH in HCe. The table provides the conversion units for subjects who are converting from dexamethasone to another GC and provides the units to convert GC mg to HCe units to conduct GC dose changes.

Note that fludrocortisone (a mineralocorticoid, not a GC) should not be converted to HCe or included in the calculation of a subject's total daily GC dose.

Table 1. Glucocorticoid Dose Conversion to Hydrocortisone Equivalents (HCe)

Glucocorticoid	Potency in CAH (HCe)
Hydrocortisone	1
Prednisone	4 ¹
Prednisolone or methylprednisolone	5 ^{1,2}
Dexamethasone	60 to 80 ³

¹[Zoorab 1998](#). ²[Clayton 2002](#). ³[Rivkees 2010; Speiser 2018](#). The Investigator may use a conversion factor for dexamethasone in the range specified, based on clinical judgment. The protocol uses a 1:4 ratio for HC:prednisone and 1:5 for HC:prednisolone. However, transitioning from prednisolone to prednisone will require the closest approximation possible given the denomination of tablets available. Switching from 1mg prednisolone to 1mg prednisone is the closest approximation possible and therefore is not a protocol deviation.

4.1.4.3 A4-Based Daily Glucocorticoid Dose Adjustment Algorithm

Any adjustment of GC dose will be based on the A4 level measured at study visits and made in increments ≤ 5 mg/day HCe according to the standardized sets of GC regimens ([Table 1](#)).

The below A4-based algorithm will be used to guide changes to GC replacement therapy. Reductions below 15 mg/day should be discussed with the Medical Monitor.

A4 Level ≤ULN

- Reduce GC dose
- GC dose reductions may begin on Week 2 (based on Day 1 measurement) and thereafter at Week 6, 12, 18, 24, 32, 40, 52, and 64 study visits, or during the optional Open-Label Extension Period

A4 Level >1.25x ULN

- Increase GC dose
- GC dose increases can occur at Week 6, 12, 18, 24, 32, 40, 52, and 64 study visits, or during the optional Open-Label Extension Period

A4 level >ULN and ≤1.25x ULN

- Maintain GC Dose

The Investigator should contact the Medical Monitor if the Investigator does not intend to follow A4-based GC dose adjustment algorithm at a visit.

The daily GC dosing frequency (e.g., BID or 3 times daily [TID]) should remain stable throughout the study. The Investigator should contact the Medical Monitor if the Investigator intends a change to the GC dosing frequency at a visit.

If a change in GC is warranted by the A4 algorithm, sites will contact subjects by telephone within 2 weeks after each applicable study visit. If no GC dose adjustment is warranted based on the A4 level, the site does not need to contact the subject.

Sites will telephone subjects again 7 days after GC dose adjustment to assess for the occurrence of AEs and the initiation of new concomitant medications.

4.1.4.4 Stress Dosing of Glucocorticoid

During times of clinically significant physical stress such as intercurrent illness with fever, surgical procedures, or significant trauma, subjects may take extra GC (in the form of HC) consistent with the “sick day guidelines” for prevention of adrenal crisis shown in [Table 2](#) ([Bornstein 2016](#)). Sites may employ variations on these guidelines, consulting with the Medical Monitor, if possible, in non-urgent situations. The Sponsor will provide all subjects with oral HC for the purposes of stress dosing ([Section 6.2.2](#)). For subjects who are not taking HC as their background GC regimen, the stress dose of HC should be estimated based on the relative potencies of GCs specified in [Table 1](#).

The stress doses recommended in [Table 2](#) are meant to *replace* a subject’s usual daily GC dose; they are NOT taken *in addition* to the subject’s usual daily GC dose. When taking the stress dose orally, the subject should take the entire stress dose using HC tablets from the bottle provided by the Sponsor. Daily replacement dosing from the subject’s or Sponsor-provided GCs should be temporarily held during stress dosing and reinstated as soon as the stress dosing period ends.

While all GC stress doses should be entered into the EDC, changes to usual daily GC dose only need to be entered into EDC when there is a definitive long-term, chronic alteration in the usual daily GC dosing regimen.

Table 2. Sick Day Guidelines for Stress Dosing of Hydrocortisone

Condition	Stress Dosing of Hydrocortisone
Home management of fever >38 °C (>100.4 °F) or illness requiring bed rest, when requiring antibiotics for an infection, or before undergoing a minor outpatient procedure (eg, dental work)	
 Approximately double the routine oral GC dose (and give as HC) until recovery (usually 2 to 3 days) For fever >39 °C (102.2 °F) only, approximately triple the routine oral GC dose (and give as HC) until recovery (usually 2 to 3 days)¹ Increase consumption of electrolyte-containing fluids and simple and complex carbohydrates (El-Maouche 2018), as tolerated
Unable to tolerate oral medication due to gastroenteritis or trauma	
 HC 100 mg IM or SC
Minor to moderate surgical stress	
 HC 25 to 75 mg/24 hours (usually 1 to 2 days)
Major surgery with general anesthesia, trauma, or disease that requires intensive care	
 HC 100 mg IV injection, followed by HC 200 mg/24 hours (via continuous IV infusion or 50 mg bolus every 6 hours IV or IM) Weight-appropriate continuous IV fluids with 5% dextrose and 0.2% or 0.45% NaCl Rapid tapering and switch to oral regimen depending on clinical state
Acute adrenal crisis	
 HC 100 mg IV injection, followed by HC 200 mg/24 hours (via continuous infusion or 50 mg every 6 hours IV or IM), reduced to HC 100 mg/day the following day Rapid infusion of 1000 mL isotonic saline within the first hour or 5% glucose in isotonic saline, followed by continuous IV isotonic saline guided by individual patient needs For hypoglycemia: 0.5 to 1 g/kg dextrose or 2 to 4 mL/kg of D25W (maximum single dose 25 g) infused slowly at rate of 2 to 3 mL/min Cardiac monitoring: rapid tapering and switch to oral regimen depending on clinical state

Abbreviations: D25W, dextrose 25% in water; GC, glucocorticoid; HC, hydrocortisone; IM, intramuscular; IV, intravenous; SC, subcutaneous.

¹ When tripling the routine oral GC dose, the HC stress dose should be rounded up to the next highest 10-mg HC tablet.

To prevent hypoglycemia, the subject should drink small amounts of clear sugar-containing liquids frequently and/or consume carbohydrates if the subject is able, glucose monitoring should be considered, and IV sodium and glucose replacement may be required ([Clayton 2002](#); [Merke and Bornstein 2005](#); [Keil 2010](#)).

Day-to-day physical or psychological stressors, such as a short-term strenuous activity or school examinations, generally do not require increased GC dosing ([Clayton 2002](#); [Crown & Lightman 2005](#); [Merke and Bornstein 2005](#)).

Subjects will maintain stress dosing until symptoms subside (or according to the clinical judgment of the treating physician), then return to their usual GC regimen. Any scheduled lab draws should be delayed until 5 to 7 days after subjects first return to their usual GC regimen. Any study visit delayed because of stress dosing will not be considered a protocol deviation. Extra unscheduled study visits for safety follow-up may be conducted in the interim.

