4.3.1.2 Glucocorticoid Dose Process and Documentation

Documentation of GC doses will be completed using eCRFs. If an adjustment in GC dose or change in distribution of daily doses is warranted, a new record will be recorded on the Prior and Concomitant Daily Glucocorticoids/Mineralocorticoids eCRF for each change.

At Weeks 24, 52 and 76 the eCRFs will record the total daily prescribed GC dose and will serve as the source for the Primary Efficacy Endpoint and GC-related change endpoints. For example, the recorded GC dose at Week 12 and the A4 assessment taken at Week 12 will be used to meet the Primary Efficacy Endpoint definition.

Based on the A4 assessment from each visit and aligning with the primary investigator's clinical judgement, the primary investigator will confirm if the GC dose level will be adjusted or maintained until the next clinic visit. For every visit with a potential adjustment in GC, the Key Glucocorticoid Dosing eCRF will record the A4 algorithm outcome (decrease, increase, maintain dose), whether the PI followed the algorithm's outcome (yes, no), reason for not following the outcome (clinical judgement, subject at physiologic dose), and the PI final decision (decrease, increase, maintain dose).

For subjects enrolled under protocol amendment 6 or earlier and prior to Week 24, the RTSM system will dispense a new GC regimen. For subjects enrolled under or after protocol amendment 7 or for visits after Week 24 for subjects enrolled under protocol amendment 6 or earlier, a new prescription will be written by the PI for the adjusted daily GC dose regimen and relayed to the subject to fill at their local pharmacy. An eCRF Glucocorticoid Medication – Received will record the date the subjects received/filled the new Sponsor-provided GC regimen and the day of first dose from the new regimen.

Reconciliation across eCRFs will be performed to ensure the accuracy of the GC dose data.

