8.3.20.4 Stress Event

A stress event is defined as an entry in the diary indicating a stress dose was taken or a record in the CM eCRF if the stress dosing was not recorded in the diary in a timely manner. Consecutive days of stress dosing are counted as a single stress event.

8.3.20.5 Cumulative GC Dose at Week 24

The cumulative GC dose from Study Day 1 to Week 24 is defined as:

- Sum of daily GC exposures (total daily dose multiplied by days on a regimen) from CM eCRF
- Sum of stress doses (HCe mg) (from CM eCRF where the indication for the stress dosing is “STRESS DOSE/DOSING”)

For subjects who discontinue study drug treatment prior to the Week 24 visit, the cumulative dose will be summed over the duration of Study Day 1 to the date of last dose of study drug.

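### The protocol requires entry only of lasting changes in usual GC dose, while the SAP's cumulative dose (endpoint 3.2) needs every change and a rule for stress days

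*Protocol*

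**What the plan says.** **Entry rules.** Protocol 4.1.4.4 sets two rules in one sentence. On stress doses it begins "While all GC stress doses should be entered into the EDC", and it goes on to say that "changes to usual daily GC dose only need to be entered into EDC when there is a definitive long-term, chronic alteration" in the regimen. Just before this, it explains that a stress dose replaces the usual dose, which "should be temporarily held during stress dosing and reinstated as soon as the stress dosing period ends".

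SAP 4.3.1.2 is broader. When the GC dose is adjusted or redistributed over the day, "a new record will be recorded on the Prior and Concomitant Daily Glucocorticoids/Mineralocorticoids eCRF for each change".

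**Use of the records.** SAP 8.3.20.5 defines cumulative dose to Week 24 (endpoint 3.2) as two components added together. The first is "Sum of daily GC exposures (total daily dose multiplied by days on a regimen) from CM eCRF". The second is the sum of stress doses in hydrocortisone equivalents (HCe). Nothing is said about subtracting the usual dose on stress days.

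**Visit doses.** SAP 4.3.1.2 states: "At Weeks 24, 52 and 76 the eCRFs will record the total daily prescribed GC dose". The primary model in SAP 12.3.3 uses dose change at Weeks 3, 6, 12, 18 and 24. The imputation models in SAP 12.3.3.1 use the interim doses, and the retrieved-dropout version uses the last available dose.

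**Checks.** At each visit with a possible adjustment, the Key Glucocorticoid Dosing eCRF captures what the A4 algorithm indicated, whether it was followed, and the final decision. SAP 4.3.1.2 adds: "Reconciliation across eCRFs will be performed to ensure the accuracy of the GC dose data".

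**The concern.** The two documents set different thresholds for entering a change in usual dose, and the SAP's calculation assumes the lower one. SAP Section 3 gives the SAP precedence for planned analyses, but sites enter data under the protocol. An analysis plan cannot recover a change that sites were told they need not enter.

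The gap is narrow. It covers a change in usual dose that is neither stress dosing nor lasting, such as an off-algorithm increase that is reversed before long. Such changes are possible: SAP 4.2.2.1 lets clinical judgement override the algorithm in all cases. If one is not entered, the days-on-regimen product carries the wrong dose for that interval. If the interval spans a visit, the interim dose may be wrong too.

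The same entry rule has a second effect. A temporary hold of usual dose is not a chronic alteration, so it need not be entered. The regimen record then runs through the stress days at full dose, and the stress dose is added on top.

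**Working it through.** The plan gives no figure for the completeness of dose records or for the expected effect on cumulative dose, so there is nothing to reproduce. The scenarios below bound the size of one episode.

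**Inputs**
- Days from Day 1 to Week 24: 24 × 7 = 168.
- Usual dose: 30 to 60 mg/day HCe, the eligibility range (Protocol 5.1.1), held constant for simplicity.
- Increment: 5 mg/day HCe, the maximum algorithm step (Protocol 4.1.4.3).
- Oral stress episode: about double the usual dose, usually for 2 to 3 days (Protocol 4.1.4.4, Table 2).
- Duration of an unrecorded change: assumed, with a range shown.

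**A. Unrecorded temporary increase (undercount)**

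Missing dose = 5 × days. Share = missing dose ÷ (usual dose × 168). The 24-week totals are 30 × 168 = 5,040 mg and 60 × 168 = 10,080 mg.

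| Days | Missing (mg) | Share at 30 mg/day | Share at 60 mg/day |
|---|---|---|---|
| 7 | 35 | 0.69% | 0.35% |
| 14 | 70 | 1.39% | 0.69% |
| 28 | 140 | 2.78% | 1.39% |
| 42 | 210 | 4.17% | 2.08% |

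A subject whose average dose falls below 30 mg/day during the trial would have a larger share. An unrecorded temporary decrease gives the same amounts with the opposite sign.

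**B. Usual dose not removed on stress days (overcount)**

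For usual dose b and d double-dose stress days:
- True total = b × (168 − d) + 2b × d = b × (168 + d).
- SAP sum = b × 168 + 2b × d.
- Excess = b × d. Relative excess = d ÷ (168 + d), whatever the usual dose.

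At b = 30 and d = 3, the true total is 30 × 165 + 60 × 3 = 5,130 mg and the SAP sum is 5,040 + 180 = 5,220 mg. The excess is 90 mg, or 90 ÷ 5,130 = 1.75%. For d = 2 it is 2 ÷ 170 = 1.18%, and for nine stress days over the period it is 9 ÷ 177 = 5.08%.

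**C. Reach into the primary analysis**

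A change that starts and ends between visits alters no visit dose. One that spans Week 3, 6, 12 or 18 could alter that visit's value. With an unstructured covariance and a treatment-by-visit term, interim values affect the Week 24 contrast mainly through subjects with no Week 24 dose, directly or by imputation.

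**The case against.** The protocol sentence stands in the stress-dosing section, straight after the rule that usual dosing is held and reinstated. Its natural purpose is to stop sites from entering that hold as a regimen change. It also sets a minimum for entry and forbids nothing. Both points are fair. They make the gap less likely to matter in practice, but they leave the conflict with the SAP's each-change rule in place, and the first reading is exactly what produces the double count on stress days.

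Several stronger conclusions are tempting and are not supported:

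- **Temporary increases in general go uncounted.** Stress doses are the main temporary increase foreseen; all are to be entered, and SAP 8.3.20.5 sums them. A4-driven steps are regimen changes and are also captured on the Key Glucocorticoid Dosing eCRF. The increase described for under-treatment in Protocol 7.1.5 is meant to last, so it would be entered.
- **No dose is recorded at interim visits.** SAP 4.3.1.2 names Weeks 24, 52 and 76 but does not say only those, and its own example mentions a recorded Week 12 dose. Protocol 1.3.4 schedules monitoring of background GC at every treatment-period visit. The source of the Week 3 to 18 analysis doses is unstated, which is a lesser point.
- **The error favours tildacerfont.** Nothing in the documents shows that unrecorded changes would differ by arm, and scenarios A and B can run in opposite directions.
- **A stated fraction of the treatment effect is artefact.** The documents give neither an expected effect on cumulative dose nor a frequency of temporary changes.

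The planned reconciliation is a partial safeguard. It compares eCRFs, so it cannot find a change entered on none of them. As SAP 4.3.1.2 describes it, the dosing-decision form records a direction and a decision, without milligrams or dates.

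**Conclusion.** The entry rules conflict, and SAP 8.3.20.5 lacks a rule for the usual dose on stress days. Together these can make cumulative GC dose wrong in either direction.

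Per subject and episode the size is modest: about 0.3% to 4.2% of the 24-week total for an unrecorded 5 mg/day change lasting 1 to 6 weeks, and about 1.2% to 1.8% for one stress episode of 2 to 3 double-dose days. These figures assume a constant usual dose of 30 to 60 mg/day. The durations in scenario A are assumptions, and the number of subjects affected is unknown, so no group-level bias can be stated.

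The consequence falls mainly on endpoint 3.2, which is exploratory and outside the Type I error procedure of SAP 9.6. Interim model doses and imputation inputs are affected at most marginally. A reader might infer that the primary result is at risk; the documents do not support that, because the Week 24 prescribed dose has its own record. The point merits correction because the repair is cheap and missing entries become harder to recover after the Week 24 lock.

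**What to change.** 1. **Entry rule.** By site memo or eCRF completion note, align Protocol 4.1.4.4 with SAP 4.3.1.2: enter every change in prescribed usual daily GC dose, of any duration, with start and stop dates; enter stress doses separately.
2. **Interim doses.** In SAP 4.3.1.2, name the source record for the Week 3, 6, 12 and 18 doses.
3. **Stress days.** In SAP 8.3.20.5, state that the usual dose is not counted on days when a stress dose replaces it.
4. **Existing data.** Before the Week 24 lock, query dose records against site source documents and the Key Glucocorticoid Dosing eCRF. The diary is only a partial check: as SAP 8.3.19.5.3 uses it, it gives adherence responses and no milligram amounts.

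The cost is one memo, two SAP sentences, and some added data entry and queries. These are changes to data capture and calculation only; no dosing rule is altered.
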